7.3. Changes in Laboratory Tests

Safety laboratory tests are scheduled to be performed during screening and first follow-up post procedure. Additional unscheduled laboratory tests would be performed as clinically indicated. Local lab will provide the results to each center.

The following safety labs are to be obtained:

- Hematology: white blood cell count (WBC), red blood cell count (RBC), hemoglobin, hematocrit, platelets, differential blood count (neutrophils, lymphocytes, monocytes, eosinophils, basophils).
- Serum chemistry: total bilirubin, AST, ALT, alkaline phosphatase (ALP), creatinine, blood urea nitrogen, sodium, potassium, chloride, bicarbonate, phosphorus, calcium, glucose, albumin.

Lab results will be tabulated based on local normal ranges [**Table 14.3.3.1.1 (hematology)**, **Table 14.3.3.1.2 (chemistry)**]. That is, the number of subjects with normal, low, or high lab results at screening (Baseline) and end of study will be cross-tabulated for IC High dose, IC Low dose and Study Overall without any inferential statistics. This analysis will include only the scheduled lab tests.

Number (%) subjects with abnormal lab results, either clinically significant, or not clinically significant (scheduled and unscheduled lab) determined by the investigator, will be tabulated by IC dose group and study overall without inferential statistics [**Table 14.3.3.2.1 (hematology)**, **Table 14.3.3.2.2 (chemistry)**].

7.4. Changes in Vital Signs

During screening and follow-up visits body temperature, pulse rate, pulse oximeter (%) respiratory rate, and blood pressure will be assessed. Blood pressure and pulse measurements should be preceded by at least 5 minutes of rest for the subject in a quiet setting without distractions (e.g., television, cell phones).

Continuous monitoring, including heart rate and rhythm, will be required during the procedure and in the immediate post-operative period, vital signs will be collected for the study at the following specific time points: immediately prior to each injection and 5 minutes after each injection and thereafter approximately every 15 minutes through 1 hour following the procedure. Investigator will determine each vital sign as normal or abnormal, and if it is abnormal, the

investigator will also determine if the abnormal vital signs is or is not clinically significant. Any clinically significant changes to vital signs or heart rhythm will be reported as an adverse event.

Vital signs data summary will be provided by treatment groups (IC High, IC Low, and Saline). Changes in vital signs will be derived for each subject at each timepoint as

$$\text{Change} = \text{Post baseline} - \text{baseline}$$

Vital signs collected on Day 1 prior to Saline injection will be the baseline vital signs if not missing; otherwise, measurements taken at screening visit will serve as the baseline.

The summary table (**Table 14.3.4.1**) will display descriptive summary of vital signs and change from baseline (sample size, mean, median, and standard deviation, range) without inferential statistics.

Number (%) subjects with abnormal vital signs, either clinically significant or not clinically significant from all vital signs assessments (scheduled and unscheduled) will be tabulated by treatment groups (IC High, IC Low, and Saline) without inferential statistics (**Table 14.3.4.2**).

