The study will enroll approximately 116 subjects from approximately 10 – 20 study centers in the United States. Subjects scheduled for urological or gynecological surgical procedures, age 18 to 85 years inclusive, will be screened for participation. Screening will occur within 30 days before study drug administration (Day of Surgery). After signing the informed consent, medical history, physical examination, baseline laboratory testing, pregnancy testing, 12-lead ECG, and vital sign measurements will be completed during the screening visit. Any procedure done for the purpose of the surgery before the date of signing the informed consent may be used as long as it was within 30 days of the scheduled surgery date.

On the day of surgery (Day 1) the subject will be evaluated for eligibility for randomization. Eligible subjects will be randomized to receive a dose of either IC high dose (5 mL) or IC low dose (2.5 mL). Each randomized subject will serve as his/her own control by receiving a dose of normal saline prior to receiving the randomized IC dose. The surgeon will be blinded to the IC dose a subject receives. Time of injection of saline and IC will be captured.

To evaluate the efficacy outcomes, each subject will first be injected intravenously with 5 mL 0.9% saline. The ureteral orifices/flow will be observed and video recorded for 10 mins. The time period that will be captured on video is from injection to 10 minutes post injection. If both ureters cannot be visualized simultaneously, then alternating 15-30 second images of each ureter or ureteral orifice will be obtained. The process will be repeated in the same patient for the IC dose. Hence, each subject will have 2 videos and each will be about 10 minutes in length.

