3.7. Treatment Group vs Randomization Group

All qualified subjects will be randomized to either a dose of 2.5 mL IC (referred to as the Low dose) or a dose of 5.0 mL IC (referred to as the High dose). All randomized subjects will receive a dose of normal saline before receiving the randomized IC dose.

Hence, there are 2 randomization groups, namely IC High Dose and IC Low Dose and 3 treatment groups (IC High dose, IC Low dose, and Saline) in this study.

If a dosing error occurred (e.g., a subject was randomized to the IC High dose but actually received IC Low dose, and vice versa), the subject will be included in the actual treatment group received for efficacy, PK, and safety analyses; this will be an important protocol deviation and the incident will be clearly documented in the study report and in the database.

Data presentation for study population, physician overall satisfaction, safety lab, and 12-ECG will be based on the 2 randomization groups; whereas the data presentation for conspicuity, TTV, adverse events, and vital signs will be based on the 3 treatment groups. A Study Overall group may be included in certain data presentations (e.g., demographics) if data warrant. The Saline group will include all subjects who had saline dose, hence, the number of subjects in this treatment group will expect to be twice the size of IC Low dose and IC High dose. If data warrants, the Saline group may also be split by IC dose group. That is, subjects received the IC Low dose vs subjects received the IC High dose.

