7.2. Adverse Events

Adverse events reported from Day 1 beginning at the Saline injection through the final follow-up will be considered treatment emergent adverse events (TEAEs). **Adverse event reported after Saline injection and prior to IC injection will be mapped to Saline treatment, all adverse events after IC injection, including events reported during the follow period will be mapped to IC treatment. For all AEs, if the onset date is missing/partial, the AE is TEAE and will be mapped to IC study unless the available portion of the date/time indicates otherwise.**

The Medical Dictionary for Regulatory Activities (Version 22) will be used to classify all AEs with respect to system organ class and preferred term.

The following summary tables will be produced for the TEAEs. All data summaries will provide number (%) subjects as well as total number of events in each category by treatment group (IC High, IC Low, and Overall).

1. a topline summary of TEAEs (**Table 14.3.2.1**)
2. a summary table by preferred term in descending order of total incidence (**Table 14.3.2.2**)
3. a summary table by system organ class and preferred term (**Table 14.3.2.3**)
4. a detailed summary table by system organ class, preferred term and severity (**Table 14.3.2.4.1**)
5. a detailed summary table by system organ class, preferred term and relationship (**Table 14.3.2.4.2**)
6. a table of serious TEAEs by system organ class and preferred term (**Table 14.3.2.5**)
7. TEAE leading to study discontinuation (**Table 14.3.2.6**)

In addition, adverse event of special interest (**Table 14.3.2.7**) will be identified and summarized if data warrant. Adverse event of special interest (AEOSI) could include but not limit to transient elevation of blood pressure and reflex bradycardia. For example, TEAE of tachycardia, hypotension, hypertension, rash or erythema, respiratory symptoms, such as dyspnea or

bronchospasm will be flagged as AEOSI. All adverse events will be reviewed before database lock to identify all AEOSI in the study.

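### Table 14.3.4.2 compares any-abnormal vital-sign percentages between Saline and IC, although the fixed sequence gives saline 1-2 scheduled readings and IC about 6-9

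*SAP*

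**What the plan says.** The order of treatment is fixed. SAP Section 3.7 states: "All randomized subjects will receive a dose of normal saline before receiving the randomized IC dose". Section 2 describes a saline injection with a video ("The time period that will be captured on video is from injection to 10 minutes post injection") and then says: "The process will be repeated in the same patient for the IC dose".

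On the day of surgery, Section 7.4 schedules vital signs "immediately prior to each injection and 5 minutes after each injection and thereafter approximately every 15 minutes through 1 hour following the procedure". The same section adds a later reading: "During screening and follow-up visits body temperature, pulse rate, pulse oximeter (%) respiratory rate, and blood pressure will be assessed". Baseline is the Day 1 measurement before saline, with screening as the fallback.

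Table 14.3.4.2 reports the number and percentage of subjects with abnormal vital signs "from all vital signs assessments (scheduled and unscheduled) will be tabulated by treatment groups (IC High, IC Low, and Saline" groups, with no inferential statistics. Its title in Section 8.1 restricts it to post-baseline values.

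Section 7.4 gives no rule assigning a reading to a treatment, no common window and no per-reading denominator. The only assignment rule in the SAP is for adverse events, in Section 7.2: "all adverse events after IC injection, including events reported during the follow period will be mapped to IC treatment".

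**The concern.** A subject counts as abnormal if any reading in the window is abnormal, so the percentage depends on how many readings the window holds. Here the sequence makes that number very different for saline and for IC. The later readings also cover the rest of the operation, recovery and the follow-up visit, none of which has a saline counterpart.

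Section 2.1.2 lists the proportion of subjects with clinically important vital-sign changes after treatment as safety endpoint 3, and Table 14.3.4.2 is the planned vital-sign table that gives subject proportions. Saline is the only non-IC reference in the trial. If its column sits next to the IC columns, readers will compare the percentages, and the difference will partly reflect how long and how often each subject was observed. The distortion runs against the product.

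**Working it through.** The plan gives no figure for this table, so there is none to reproduce. The check counts readings and then asks what the table would show if IC had no effect.

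**Step 1. Scheduled post-baseline readings (Section 7.4 schedule)**

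- Saline: the reading 5 minutes after injection, plus the reading just before IC if that is credited to saline. This gives 1-2. It takes the saline period to be about 10 minutes, which is the video length; the actual interval to IC is not stated. If IC came 20 minutes or more after saline, a further 15-minute reading could fall under saline.
- IC, Day 1: 5 minutes after injection, then every 15 minutes until 60 minutes after the procedure ends. The follow-up visit adds one.

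| Procedure ends, minutes after IC | Day 1 reading times (min) | Day 1 | With follow-up |
|---|---|---|---|
| 10 | 5, 20, 35, 50, 65 | 5 | 6 |
| 30 | 5, 20, ..., 80 | 6 | 7 |
| 60 | 5, 20, ..., 110 | 8 | 9 |

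An end earlier than 10 minutes would not fit the IC video. Crediting all post-IC readings to IC is an inference for vital signs.

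**Step 2. Probability of at least one abnormal reading, with no drug effect**

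Let p be the chance that a single reading is abnormal, the same in both windows, and k the number of readings.

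- Independent readings: 1 - (1 - p)^k.
- Correlated readings: beta-binomial with intraclass correlation ρ, a = p(1 - ρ)/ρ, b = (1 - p)(1 - ρ)/ρ. The probability is 1 - B(a, b + k)/B(a, b), where B is the beta function.

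The documents give neither p nor ρ, so both are assumptions shown over a range. At p = 0.05 and independence, saline with 2 readings is 1 - 0.95² = 9.8% and IC with 6 is 1 - 0.95⁶ = 26.5%.

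With 2 saline and 6 IC readings at p = 0.05:

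| ρ | Saline | IC |
|---|---|---|
| 0 | 9.8% | 26.5% |
| 0.3 | 8.3% | 15.7% |
| 0.6 | 6.9% | 10.1% |
| 0.9 | 5.5% | 6.1% |

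**Step 3. Sensitivity**

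- One saline reading instead of two: saline is 5.0% at every ρ.
- Nine IC readings: 37.0% if independent, 18.9% at ρ = 0.3.
- Other per-reading rates, 2 versus 6, independent: p = 0.02 gives 4.0% versus 11.4%; p = 0.10 gives 19.0% versus 46.9%.
- A low rate, p = 0.005, independent: 1.0% versus 3.0%.
- Break-even at p = 0.05 under IC, independent: saline would need 1 - (0.95⁶)^(1/2) = 1 - 0.95³ = 14.3% per reading for the columns to match.

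**Step 4. After matching**

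With one 5-minute reading in each window, both columns are expected to show 5.0% at p = 0.05, whatever ρ is.

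**The case against.** The strongest reply is that the table is only descriptive and is not the only display. Section 7.4 specifies no inferential statistics, and no decision rule uses the table. Table 14.3.4.1 gives values and changes from baseline by timepoint for the same three groups. A reader can therefore compare the 5-minute post-saline and post-IC blood pressure and pulse directly. This stands. One might infer that an early effect, such as the transient blood pressure rise or reflex bradycardia named in Section 7.2, could not be seen at all; the planned tables do not support that. What Table 14.3.4.1 does not give is abnormal counts, so it does not correct the proportions.

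A second reply is that the SAP never says that all later vital signs belong to IC. That is so: the explicit rule covers adverse events only. But a by-treatment table in a fixed sequence needs some rule, and assigning readings to the most recent injection is the natural one. The silence itself needs fixing.

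A third is that the size depends on assumed inputs. Readings 15 minutes apart in one patient are unlikely to be independent, and the gap nearly closes when correlation is very high. If the Section 8.1 title governs and only clinically significant abnormalities count (the Section 7.4 text counts both kinds), the per-reading rate could be well below 5%. This limits the magnitude, not the direction.

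It is tempting to extend the point to adverse events, where about 30 days against about 10 minutes is a ratio of 30 × 1,440 / 10 = 4,320. Section 7.2, however, lists the TEAE columns as IC High, IC Low and Overall, with no Saline column. Sections 3.7 and 7 do speak of adverse events by treatment group, but that ratio biases no display listed in Section 7.2.

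**Conclusion.** The point holds for Table 14.3.4.2. As written, its Saline and IC percentages are not comparable: with equal per-reading risk, the IC columns are expected to be higher in every scenario examined. The gap runs from under 1 percentage point (2 versus 6 readings, 5% per reading, correlation 0.9) to about 17 points (same counts and rate, independent). At correlation 0.3 it is about 7 points.

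This rests on post-IC readings being credited to IC, a saline period of about 10 minutes, a procedure ending 10-60 minutes after IC, and assumed rates and correlations. The larger saline group does not help, because each percentage uses its own denominator. Unscheduled readings would widen the gap if most fall in the longer IC window.

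The consequence is a misleading display of safety endpoint 3. It is not a false test result, and the randomized High-versus-Low comparison is unaffected. The change is worth making because it is cheap and specific.

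**What to change.** In SAP Section 7.4:

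1. State the rule that assigns each vital-sign reading to a treatment, including the reading just before IC, unscheduled readings and the follow-up visit.
2. Base the saline-versus-IC columns of Table 14.3.4.2 on the matched scheduled timepoint only: the 5-minute reading after each injection, in subjects who have both.
3. Show abnormal counts from later intra-operative, recovery, unscheduled and follow-up readings in separate rows for IC High and IC Low only, labelled as having no saline comparator.
4. Add a note that saline always precedes IC, so a period effect remains even in the matched rows.

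No new adverse event table is needed. At most, Section 7.2 could state that TEAEs mapped to saline and to IC cover unequal windows and are not to be compared.

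The cost is SAP wording and one re-cut of readings already scheduled, with no added procedures. The matched rows will contain fewer events, and matching removes the reading-count artefact but not the order effect.

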7.5. Changes in 12-Lead ECG

During screening and first post procedure follow-up visit, 12-lead ECG will be assessed. ECG interpretation will include normal, abnormal but not clinically significant; abnormal and clinically significant.

Number (%) subjects in each results interpretation category at each time point will be tabulated by randomization group (IC High, IC Low) and study overall, including shift from normal to abnormal at end of study without any inferential statistics (**Table 14.3.5**).

Other 12-Lead ECG related parameters, including PR interval, RR interval, QRS duration, QT interval, and QTc interval, will also be collected. Those parameters will not be tabulated, but data listings will be provided.

8. TABLE OF CONTENTS OF PLANNED DATA SUMMARIES

8.1. Summary Tables

Table No.	Table Title	Analysis Set
14.1.1.1	Disposition Summary by Randomization Group	Enrolled Analysis Set
14.1.1.1	Number of Randomized Subjects by Site for each Analysis Set	ITT Analysis Set
14.1.2.1	Demographics, Baseline Characteristics, and Study Surgery Characteristics by Randomization Group	Safety Analysis Set
14.1.2.2	Demographics, Baseline Characteristics, and Study Surgery Characteristics by Randomization Group	mITT Analysis Set
14.1.3	General Medical History and Surgical History by Randomization Group	Safety Analysis Set
14.1.4	Summary of Protocol Deviations by Randomization Group	Safety Analysis Set
14.1.5	Summary of Concomitant Medications by Drug Class and Medication Preferred Name	Safety Analysis Set
14.2.1.1	Treatment Effect on Conspicuity Score Based on Central Readers Assessment - An Observed Data Analysis	mITT Analysis Set
14.2.1.2	Treatment Effect on Conspicuity Score Based on Central Readers Assessment – Sensitivity Analysis 1	mITT Analysis Set
14.2.1.3	Treatment Effect on Conspicuity Score Based on Central Readers Assessment – Sensitivity Analysis 2	The Best-Case Scenario
14.2.1.4	Treatment Effect on Conspicuity Score Based on Central Readers Assessment – Sensitivity Analysis 3	The Worst-Case Scenario
14.2.2	Physician Overall Satisfaction Assessment with IC Treatment	mITT Analysis Set
14.2.3.1	Proportion of Responders to IC Treatment Based on Central Readers Assessment - An Observed Data Analysis	mITT Analysis Set
14.2.3.2	Proportion of Responders to IC Treatment Based on Central Readers Assessment - A Sensitivity Analysis	The Worst-Case Scenario
14.2.4	Time (minutes) from the Start of Injection to Adequately Visualized Blue Color in the Ureter Jet Flow After IC Treatment	mITT Analysis Set
Repeat 14.2.1 to 14.2.4 for efficacy per Protocol set if $\geq 10\%$ of MITT subjects are excluded from the efficacy per Protocol analysis set		
14.2.5.1	Treatment Effect on Conspicuity Based on Surgeons Assessment	mITT Analysis Set
14.2.5.2	Analysis of Evaluator Effect as a Covariate on Conspicuity	mITT Analysis Set

Table No.	Table Title	Analysis Set
14.2.5.3	Dichotomized Concordance between Surgeons and Central Readers Assessment of Conspicuity	miITT Analysis Set
14.3.2.1	Topline Summary of Treatment Emergent Adverse Event	Safety Analysis Set
14.3.2.2	All TEAE by Preferred Term Displayed the Most Commonly Reported Event First –	Safety Analysis Set
14.3.2.3	TEAE by SOC and Preferred Term	Safety Analysis Set
14.3.2.4.1	TEAE by SOC, Preferred Term and Severity	Safety Analysis Set
14.3.2.4.2	TEAE by SOC, Preferred Term and Relationship to Study Drug	Safety Analysis Set
14.3.2.5	All Serious TEAE by SOC and Preferred Term	Safety Analysis Set
14.3.2.6	TEAEs Leading to Study Discontinuation by SOC and Preferred Term	Safety Analysis Set
14.3.2.7	TEAE of Special Interest by Category and Preferred Term	Safety Analysis Set
14.3.3.1.1	Cross Tabulation of Hematology Test Results Relative to Normal Range at Baseline and Post Baseline	Safety Analysis Set
14.3.3.1.2	Cross Tabulation of Chemistry Test Results Relative to Normal Range at Baseline and Post Baseline	Safety Analysis Set
14.3.3.2.1	Summary of Subjects with Clinically Significant Abnormal Hematology Test at Post Baseline	Safety Analysis Set
14.3.3.2.2	Summary of Subjects with Clinically Significant Abnormal Chemistry Test at Post Baseline	Safety Analysis Set
14.3.4.1	Summary of Vital Signs Results and Change from Baseline by Timepoint	Safety Analysis Set
14.3.4.2	Summary of Subjects with Clinically Significant Abnormal Vital Signs Post Baseline	Safety Analysis Set
14.3.5	Summary of 12-Lead ECG Results by Interpretation Category and Timepoint	Safety Analysis Set

8.2. Figures

Figure No.	Figure Title	Analysis Set
14.2.2.1	Kaplan-Meier Survival Curves of Time to Visualization	miITT Analysis Set
14.2.2.2	Kaplan-Meier Survival Curves of Time to Visualization by Ureter	miITT Analysis Set

8.3. Data Listings

Listing No.	Listing Title	Analysis Set
16.2.1.1	Disposition	ITT Analysis Set
16.2.1.2	Analysis Population	ITT Analysis Set
16.2.2	Demographics and Baseline Characteristics	Safety Analysis Set
16.2.3	Medical and Surgical History	Safety Analysis Set
16.2.4	Study Drug Administration	Safety Analysis Set
16.2.5	Study Surgery	Safety Analysis Set
16.2.6	Protocol Deviations	Safety Analysis Set
16.2.7.1	Prior and Concomitant Medications	Safety Analysis Set
16.2.7.2	Other Procedures During Study	Safety Analysis Set
16.2.8.1	Conspicuity Score - Surgeon's Assessment and Videography Information	Safety Analysis Set
16.2.8.2	Conspicuity Score and IC treatment Responder per Central Reader's Assessment	Safety Analysis Set
16.2.8.3	Concordance Response Variable between Surgeon's and Central Reader's Assessment of conspicuity	Safety Analysis Set
16.2.8.4	Time to Visualization After IC Treatment	Safety Analysis Set
16.2.8.5	Physician Overall Satisfaction with IC Treatment	Safety Analysis Set
16.2.10.1	All Adverse Events Reported in the Study	Safety Analysis Set
16.2.10.2	Adverse Events from Subjects Who Had >=1 Serious Adverse Event	Safety Analysis Set

Listing No.	Listing Title	Analysis Set
16.2.10.3	TEAEs Leading to Study Discontinuation	Safety Analysis Set
16.2.11.1	All Hematology Test Results	Safety Analysis Set
16.2.11.2	All Chemistry Test Results	Safety Analysis Set
16.2.11.3	Urine Pregnancy Test	Safety Analysis Set
16.2.12.1	Vital Signs Results	Safety Analysis Set
16.2.13	12-Lead ECG Results	Safety Analysis Set
16.2.14	Telephone Follow-up	Safety Analysis Set
